## **STATEMENT OF COMPLIANCE**

The study will be carried out in accordance with Good Clinical Practice (GCP) as required by the following:

- United States (US) Code of Federal Regulations (CFR) applicable to clinical studies (45 CFR Part 46, 21 CFR Part 50, 21 CFR Part 56, and 21 CFR Part 312)
- International Conference on Harmonisation (ICH) E6
- National Institutes of Health (NIH) Clinical Terms of Award

All key personnel have completed Human Subjects Protection Training.

---

## LIST OF ABBREVIATIONS

ACR	American College of Rheumatology
ADRB2	Adrenergic receptor $\beta$ 2
ADRB3	Adrenergic receptor $\beta$ 3
AE	Adverse event
APS	Average pain sensitive
AUDIT	Alcohol Use Disorders Identification Test
CFR	Code of Federal Regulations
CMP	Clinical Monitoring Plan
COMT	Catechol-O-methyltransferase
CROMS	Clinical Research Operations and Management Support
CSQ-R	Coping Strategies Questionnaire Revised
DCC	Data coordinating center
DC/TMD	Diagnostic Criteria for Temporomandibular Disorder
DNA	Deoxyribonucleic acid
DSMB	Data and Safety Monitoring Board
ECG	Electrocardiogram
EDC	Electronic data capture
FDA	Food and Drug Administration
FDAAA	Food and Drug Administration Amendments Act of 2007
GCP	Good Clinical Practice
GCPS	Graded Chronic Pain Scale
GWAS	Genome-Wide Association Studies
HIT-6	Headache Impact Test
HPS	High pain sensitive
ICH	International Conference on Harmonisation
ICMJE	International Committee of Medical Journal Editors
IND	Investigational New Drug (Application)
IRB	Institutional Review Board
LPS	Low pain sensitive
MOP	Manual of Procedures
NIDCR	National Institute of Dental and Craniofacial Research
NIH	National Institutes of Health
NRS	Numeric rating scale
NSAID	Nonsteroidal anti-inflammatory drug
OCTOM	Office of Clinical Trials and Operations Management
OHRP	Office of Human Research Protection
PGIC	Patient Global Impression of Change
PI	Principal Investigator
PPT	Pressure pain threshold
SAE	Serious adverse event
SCL-90R	Symptom Checklist 90-Revised

---

SF-12 v2	Short Form 12 Health Survey Version 2
TENS	Transcutaneous electrical nerve stimulation
TMD	Temporomandibular disorder
TMJ	Temporomandibular joint
UB	University at Buffalo
UF	University of Florida
UNC	University of North Carolina
UP	Unanticipated problem
US	United States

## PROTOCOL SUMMARY

Title:	Effect of COMT Genetic Polymorphisms on Response to Propranolol Therapy in Temporomandibular Disorder
Short Title:	Study of Orofacial Pain and PropRANOlol (SOPPRANO)
Précis:	
A total of 200 participants of either sex and any race or ethnicity, recruited at 3 clinical sites, aged 18 to 65 years with chronic temporomandibular disorder (TMD), will be randomized in a 1:1 ratio to propranolol or placebo in a parallel-group, blinded clinical trial. Participants will attend 6 clinic visits over a period of 12 to 15 weeks.
 
Potential participants will be prescreened by telephone or at a clinic visit. During the Screening and Baseline Visit, participants will be consented, evaluated for eligibility, and assessed for baseline characteristics. Baseline procedures will include clinical tests and examinations and the administration of questionnaires. Additional questionnaires will be distributed to be completed and returned at the following visit.
 
At the Randomization and Titration Visit, participants will be randomized to propranolol or placebo and will begin a 10-week drug treatment phase that is divided into 1 week of drug titration, 8 weeks of drug maintenance, and 1 week of drug tapering. During treatment, many of the baseline assessments will be repeated. The final study visit will occur 1 week after drug tapering ends.
 
The primary endpoint will be a weekly pain index derived from a daily symptom diary. Secondary endpoints will be additional ratings of clinical pain; examiner assessments of experimental pain sensitivity; participant ratings of physical function, emotional function, and global improvement; occurrence of symptoms and adverse events (AEs); and use of rescue medications. DNA analyses will be conducted to identify polymorphisms in the gene that encodes catechol-O-methyltransferase (COMT), an enzyme that metabolizes catecholamines such as epinephrine, norepinephrine, and dopamine, and is associated with responses to pain.

Objectives:	The primary objective is to investigate the efficacy of extended-release propranolol compared with placebo in the reduction of a pain index in participants with TMD at week 9 of treatment (at

Visit 4).

The secondary objectives are as follows:

- To investigate gene-by-treatment group interaction to determine whether the efficacy of extended-release propranolol in the reduction of the pain index varies according to participants' polymorphisms in the coding region of the *COMT* gene.
- To investigate the efficacy of extended-release propranolol compared with placebo using secondary endpoints.

The exploratory objectives are as follows:

- To investigate whether the efficacy of extended-release propranolol in the reduction of the pain index varies according to participants' polymorphisms in 3 other genetic regions.
- To investigate whether the efficacy of extended-release propranolol in the reduction of the pain index varies according to various phenotypic characteristics.
- To collect and archive biospecimens for future biological and statistical analyses.

**Population:** 200 participants of either sex and any race or ethnicity between 18 and 65 years of age (inclusive) with chronic TMD will be randomized

**Phase:** Phase II

**Number of Sites:** Three clinical sites:

- University of North Carolina School of Dentistry at Chapel Hill, NC
- University of Florida College of Dentistry, Gainesville, FL
- University at Buffalo School of Dental Medicine, Buffalo, NY

[figure not shown]
**Study Duration:** Approximately 3 years

[figure not shown]
**Participant Duration:** 12 to 15 weeks

**Description of Agent:** Propranolol hydrochloride extended-release in 60 mg capsules taken orally twice a day over a 10-week treatment period

**Enrollment Duration:** Approximately 2 years

**Figure 1: Schematic of Study Design**

Visit 5  
Day 77 + 7

**Final Assessments**

Obtain history and Symptom Inventory, document.  
Collect and assess daily symptom diaries and drug  
containers. Assess AEs. Perform urine pregnancy  
test (females). Administer Pain Questionnaire.

## **2 INTRODUCTION: BACKGROUND INFORMATION AND SCIENTIFIC RATIONALE**

### **2.1 Background Information**

#### **2.1.1 Background on Temporomandibular Disorder**

The term “temporomandibular disorder” (TMD) encompasses all musculoskeletal disorders of the masticatory system. Common TMDs include myalgia, arthralgia, temporomandibular joint (TMJ) disc displacements with and without reduction, and TMJ degenerative joint diseases. A recent study reported that the most prevalent TMD diagnostic group is muscle dysfunction. TMD is among the most common chronic musculoskeletal pain conditions and has significant societal costs. The prevalence of TMD ranges from 6% to 12% in the general population. Overall, TMD results in 17.8 million lost work days per year for every 100 million working adults in the US. Chronic TMD is associated with substantial disability and suffering, and it negatively impacts the quality of life. Jaw pain is the most common symptom that compels patients to seek treatment. One study reported an average TMD pain intensity rating of 4.3 on a 11-point scale, similar to the averages reported for chest pain and back pain. In addition to facial pain, TMD patients frequently report various comorbid idiopathic pain conditions such as headaches, low back pain, and fibromyalgia. Novel approaches to TMD therapy are urgently needed to improve clinical outcomes and reduce the economic impact of this debilitating disorder.

#### **2.1.2 Current Pharmacologic Management of TMD**

Although there is currently no medicinal product labeled by the Food and Drug Administration (FDA) specifically for the management of TMD, several classes of drugs are used to attempt to relieve TMD-associated pain, such as nonsteroidal anti-inflammatory drugs (NSAIDs), corticosteroids, benzodiazepines, sedative hypnotics, muscle relaxants, opioids, antidepressants, and anticonvulsants. However, evidence clearly establishing efficacy and safety of these drugs in the management of TMD is scarce. The justification for their use is often based on uncontrolled clinical reports claiming efficacy, poorly controlled clinical trials, or clinical trials in other pain disorders (e.g., acute postsurgical dental pain, arthritic pain, chronic lower back pain, and neuropathic pain). There is a growing need for controlled clinical trials in the TMD population.

#### **2.1.3 Adrenergic System in Pathophysiology of TMD**

The physiological mechanisms responsible for TMD symptoms are poorly understood. A growing body of evidence suggests that enhanced  $\beta$ -adrenergic drive contributes to the pathogenesis of TMD and other complex persistent pain conditions. For example, individuals

with myofascial pain conditions have elevated catecholamine levels and augmented sympathetic responses to stressors. Additionally, fibromyalgia patients have higher basal norepinephrine levels and exaggerated norepinephrine responses to the proinflammatory cytokine, interleukin-6. In animal models, epinephrine produces mechanical hyperalgesia and sensitized cultured dorsal root ganglion neurons via action at a  $\beta$ -adrenergic receptor.

While increased  $\beta$ -adrenergic drive appears to heighten pain,  $\beta$ -adrenergic antagonists can reduce clinical pain and/or nociceptive sensitivity. A recent study of a single-dose infusion of propranolol in TMD and fibromyalgia patients revealed a short-term improvement in clinical pain ratings. The mixed  $\beta$ -adrenergic receptor/5-hydroxytryptamine (HT)1A presynaptic receptor antagonist pindolol was similarly efficacious in alleviating the cardinal symptoms of fibromyalgia, namely pain, stiffness, and nonrestful sleep. In a rodent model of TMD, both the nonselective  $\beta$ -adrenergic receptor antagonist propranolol and a selective  $\beta_2$ -blocker impaired pain behavior. In addition, the intramuscular injection of low-dose propranolol in rats reduced inflammatory pain associated with carrageenan-induced inflammation of the gastrocnemius muscle.

#### **2.1.4 Background on Propranolol**

The study hypothesis is that low-dose therapy with the nonselective  $\beta$ -adrenergic receptor antagonist propranolol will provide an efficacious and safe treatment for painful TMD. Extended-release propranolol is approved for the treatment of hypertension, angina pectoris due to coronary atherosclerosis, migraine, and hypertrophic subaortic stenosis. It has well-studied pharmacodynamic and pharmacokinetic characteristics and side-effect profile. Peak blood level following dosing with an extended-release formulation of propranolol hydrochloride occurs at approximately 6 hours, and the apparent plasma half-life is approximately 10 hours. Data from our preliminary study suggest that low-dose short-acting propranolol produces minimal side effects (e.g., mild nausea, diarrhea, and fatigue occurred at similar rates during propranolol and placebo treatment).

#### **2.1.5 Background on Catechol-O-Methyltransferase as a Genetic Marker of Response to Propranolol**

Abnormalities in catecholamine physiology are associated with diminished activity of catechol-O-methyltransferase (COMT), a ubiquitously expressed enzyme that metabolizes catecholamines such as epinephrine, norepinephrine, and dopamine. TMD patients exhibited lower COMT activity relative to pain-free controls. Our group and others have shown that various functional polymorphisms in the COMT gene that result in 3- to 15-fold reductions in COMT activity are associated with fibromyalgia, migraine, experimental pain sensitivity, and increased morphine efficacy in cancer pain treatment.

Three major haplotypes of COMT, designated as low pain sensitive (LPS), average pain sensitive (APS), and high pain sensitive (HPS), accounted for 11% of variability in experimental

pain sensitivity in women. The LPS haplotype produces higher levels of COMT enzymatic activity than the APS or HPS haplotypes. In our recent prospective cohort study, the presence of even a single LPS haplotype was found to diminish the risk of developing TMD as much as 2.3-fold. To identify the receptor mechanism whereby elevated catecholamine levels resulting from reduced COMT activity modulate pain sensitivity, our group conducted a set of behavioral pharmacologic studies in rats receiving a COMT inhibitor. We found that COMT inhibition enhanced mechanical and thermal pain sensitivity comparable to that produced by carrageenan, a chemical well known for its ability to sensitize nociceptors and increase pain behavior. COMT-related mechanical and thermal hyperalgesia was blocked by propranolol or by combined administration of selective  $\beta_2$ - and  $\beta_3$ -adrenergic receptor antagonists but not by dopaminergic,  $\alpha$ -, or  $\beta_1$ -adrenergic antagonists, suggesting that the hyperalgesia is selectively mediated by a  $\beta_{2/3}$ -adrenergic mechanism.

We hypothesize that individuals with lower COMT activity, such as those not carrying the LPS haplotype, will experience relatively greater reduction in TMD pain from propranolol therapy than individuals with other *COMT* haplotypes that confer greater COMT activity. Genotyping of the *COMT* gene will allow us to evaluate this hypothesized gene-by-treatment group interaction, potentially identifying a subset of TMD patients most likely to benefit from propranolol treatment.

## 2.2 Rationale

A randomized, double-blind, placebo-controlled, crossover pilot study with a 1-week treatment with propranolol (20 mg twice a day) has been completed in patients with painful TMD. In this study, the number of patients reporting a reduction in pain intensity rating was greater during propranolol treatment ( $p = 0.014$ ) compared with placebo. Propranolol also significantly reduced the composite pain index ( $p = 0.02$ ), but did not decrease other clinical and experimental pain ratings. When stratified by the *COMT* high-activity haplotype (LPS), a beneficial effect of propranolol on pain perception was noted in participants not carrying this haplotype, a diminished benefit was observed in the heterozygotes, and no benefit was noted in the LPS homozygotes; this effect was statistically significant in many pain measures. In the present trial, the duration of therapy for TMD with propranolol will be extended to 10 weeks, an extended-release instead of short-acting formula of the drug will be administered to enhance patient compliance over a longer treatment period, and the propranolol extended-release dose will be increased to 60 mg twice a day. Additionally, a parallel instead of crossover design will be utilized to reduce the drop-out rate and avert potential carryover effects.

Consensus recommendations for clinical trials of pain from the IMMPACT group encourage investigators to evaluate five outcomes related to pain: (1) pain; (2) physical functioning; (3) emotional functioning; (4) participant global ratings of improvement; and (5) symptoms and adverse events (AEs). They also encourage investigators to collect data to permit reporting of study conduct consistent with the recommendations of the CONSORT group. Accordingly, this protocol proposes endpoints and data recording that will address the requirements of both sets of recommendations.

## 2.3 Potential Risks and Benefits

### 2.3.1 Potential Risks

**Investigational Drug.** The investigational product is propranolol hydrochloride extended-release capsules. Propranolol has been available commercially for over 40 years and is routinely used to treat hypertension, migraine, and essential tremor at doses much greater than will be administered in this study. As propranolol is FDA approved for many disorders and has well-characterized pharmacological and side effects profiles, the risks for TMD patients using this drug at the proposed dose are low.

The package insert for propranolol hydrochloride extended-release capsules is shown in Appendix B. Propranolol is contraindicated in patients with cardiogenic shock, sinus bradycardia and greater than a first degree block, bronchial asthma, and known hypersensitivity to propranolol hydrochloride. Additionally, propranolol is not recommended for use in patients with cardiac failure, nonallergic bronchospasm, major surgery, diabetes, thyrotoxicosis, or Wolff-Parkinson-White syndrome. Patients with the above-listed conditions will not be included in the study. At all clinic visits after Prescreening, resting blood pressure and heart rate will be monitored. A 12-lead electrocardiogram (ECG) will be performed at the Screening and Baseline Visit. The ECG will be reviewed by a cardiologist who will determine the clinical significance of any ECG abnormalities. Participants will be asked to report any planned surgical procedures to the study principal investigators (PIs) since propranolol hydrochloride extended-release may increase the risks associated with general anesthesia and surgical procedures.

In a study in which male and female rats were exposed to propranolol hydrochloride in their diets, from 60 days prior to mating and throughout pregnancy and lactation for two generations, there were no effects on fertility. Contraception in males will not be required in this study. However, there are no adequate and well-controlled studies of propranolol in pregnant women.

Pregnancy is an exclusion criterion and a participant discontinuation criterion in this study. A pregnancy test will be conducted on all women of childbearing potential at all visits. In addition, propranolol is excreted in human milk; therefore, nursing is an exclusion criterion for this study.

Cardiovascular, central nervous system, gastrointestinal, allergic, respiratory, hematologic, autoimmune, skin and mucous membranes, and genitourinary AEs have been observed in patients using propranolol. All reportable AEs will be collected from the Screening and Baseline Visit through the last clinic visit.

**Electrocardiogram.** Electrode stickers placed on the participant's skin may cause discomfort when removed. Trained personnel will conduct the procedure.

---

**Questionnaires.** A participant may experience discomfort associated with being asked personal questions about her or his health history, symptoms, or emotional feelings. Participants will be told that they may choose not to answer any questions that cause discomfort.

**TMD Examination and Psychophysical Tests.** Four assessments of this kind will be performed: the TMD examination (Section 7.1.6), tests for heat sensitivity (Section 7.1.7), tests for pressure pain threshold (PPT) (Section 7.1.8), and a manual tender point examination (Section 7.1.9). Assessments of muscle and TMJ sensitivity to digital palpation during the TMD examination, responses to masticatory muscle pressure threshold tests, and responses to painful heat stimuli are designed to evoke brief pain or discomfort during application of the stimulus; however, none of these assessments are expected to result in lasting discomfort or damage to affected tissues. Transient redness or tenderness of skin is possible after tests. All testing modalities will be conducted within a range of stimulus intensities that produce a level of pain or discomfort that is acceptable to the participant. No test will exceed this range, and all tests will end upon completion of the modality or upon the participant's request, whichever comes first.

**Blood Collection.** There is a possibility of mild pain and bruising associated with a blood draw. Trained personnel will perform the blood collection using standard procedures.

**Violation of Confidentiality.** The risk of violation of confidentiality exists because human participants are providing personal information, including genetic data. Procedures to minimize risks to confidentiality are described in Section 14.4.

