## 4.2 Participant Exclusion Criteria

A potential participant who meets any of the following criteria will be excluded from enrollment and randomization:

- 1) Has a history of congestive heart failure or the presence of any of the following cardiovascular conditions: clinically significant abnormal 12-lead ECG, sinus bradycardia (resting heart rate below 55 beats per minute although lower heart rates will be acceptable upon the review and approval by the site cardiologist), greater than first degree heart block, coronary artery disease, uncontrolled hypertension, or hypotension (systolic blood pressure below 90 mm Hg). In individuals with a heart rate below 55 beats per minute, the site cardiologist will review the participant's medical history, including any concomitant medications, to ensure that they are in good general health and have no medical contraindications to taking propranolol.
- 2) Has any of the following medical conditions: bronchial asthma, nonallergic bronchospasm (chronic obstructive pulmonary disease and emphysema), renal failure or dialysis, diabetes mellitus, hyperthyroidism, fibromyalgia, or uncontrolled seizures
- 3) Has known hypersensitivity to propranolol or components of the placebo capsules
- 4) Currently taking a  $\beta$ -blocker or medication that may interact with propranolol, including haloperidol, intravenous verapamil, and catecholamine-depleting drugs, such as reserpine, within 30 days prior to the Screening and Baseline Visit
- 5) Currently taking an opioid medication, whether episodically or daily, within 30 days prior to the Screening and Baseline Visit
- 6) Has commenced a new daily prescription medication for the management of pain within 30 days prior to the Screening and Baseline Visit

---

\* one standard drink is defined as 12 ounces of regular beer, 5 ounces of wine, or 1.5 ounces of 80 proof distilled spirits.

---

- 7) Used any injection therapy (e.g., tender or trigger point injections, steroid injections) for the management of pain within 2 weeks prior to the Screening and Baseline Visit
- 8) Used acupuncture, biofeedback, or TENS for the management of pain within 2 weeks prior to the Screening and Baseline Visit
- 9) Has commenced occlusal splint therapy for the management of facial pain within 30 days prior to the Screening and Baseline Visit
- 10) Has experienced facial trauma or orofacial surgery within 6 weeks prior to the Screening and Baseline Visit

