- 11) Is undergoing current active orthodontic treatment (passive retainers are permitted)
- 12) Has a history of major depression or other major psychiatric disorder requiring hospitalization within the last 6 months prior to the Screening and Baseline Visit
- 13) Has a history of treatment for drug or alcohol abuse within the last year
- 14) Has scored 8 or more on the Alcohol Use Disorders Identification Test (AUDIT) at the Screening and Baseline Visit
- 15) Currently smokes at least 25 cigarettes per day
- 16) Currently being treated with chemotherapy or radiation therapy
- 17) Has been treated with another investigational drug or treatment within 30 days prior to the Screening and Baseline Visit
- 18) Is pregnant or nursing
- 19) Anything that, in the opinion of the investigator, would place the participant at increased risk or preclude the participant's full compliance with or completion of the study

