## **4.4 Treatment Assignment Procedures**

### **4.4.1 Randomization Procedures**

Prior to randomization, the inclusion and exclusion criteria will be reviewed, and any participant who does not meet the criteria will be discontinued from the trial. Randomization will be stratified across 3 clinical sites for a total of 200 randomized participants. Within each site, participants will be randomized in a 1:1 ratio of active drug to placebo within prespecified blocks. Randomization will be accomplished by a web-based randomization system developed and maintained by the data coordinating center. At the time of randomization, study staff, who will remain blinded to treatment assignment, will access the system, enter the participant's study identification number, and verify that the participant is eligible for randomization. The system will assign a randomization code that will indicate to the pharmacy the participant's treatment assignment.

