#### **4.4.4 Reasons for Participant Withdrawal**

Participants are free to withdraw from participation in the study at any time, and the investigator may withdraw a participant for any of the following reasons:

- Withdrawal of consent.
- Does not meet criteria for randomization.
- Pregnancy.
- Continued participation deemed to be not in the participant's best interest.
- Investigator discretion.

Participants requiring significant surgery will be withdrawn from the protocol. Investigators will use discretion in making this determination. Participants withdrawn after randomization will not be replaced. If a participant does not return for a scheduled visit, every effort should be made to contact the participant and document the outcome. If the participant withdraws consent, no further evaluations will be performed, and no attempts will be made to collect additional data.

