## **14.12 Protocol Deviations**

A protocol deviation is any noncompliance with the clinical trial protocol, GCP, or the MOP. The noncompliance may be on the part of the participant, the investigator, or the study site staff. All protocol deviations will be promptly reported within the EDC system and to the NIDCR program official. Protocol deviations will also be reported to the IRBs and the DSMB according to their guidelines. As a result of deviations, corrective actions will be developed by the site(s) and implemented promptly.

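### Protocol Section 2.3.1 says patients with Wolff-Parkinson-White syndrome will be kept out, but none of the 19 exclusions in Section 4.2 names the syndrome

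*Protocol*

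**What the plan says.** Protocol Section 2.3.1 gives two lists. The first contains the contraindications. The second contains six conditions in which propranolol is not recommended, and it ends with "major surgery, diabetes, thyrotoxicosis, or Wolff-Parkinson-White syndrome". The next sentence covers both lists without qualification: "Patients with the above-listed conditions will not be included in the study".

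The step that decides entry is in Section 4.4.1: "Prior to randomization, the inclusion and exclusion criteria will be reviewed", and anyone who fails them leaves the trial. Section 4.2 holds 19 numbered exclusions. Two could reach a patient with Wolff-Parkinson-White syndrome, although neither names it:

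- Criterion 1, the cardiovascular item, begins: "Has a history of congestive heart failure or the presence of any of the following cardiovascular conditions: clinically significant abnormal 12-lead ECG". It goes on to sinus bradycardia (rate below 55, unless the site cardiologist approves), heart block beyond first degree, coronary artery disease, uncontrolled hypertension and hypotension.
- Criterion 19 is the general clause: "Anything that, in the opinion of the investigator, would place the participant at increased risk".

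On the ECG at Visit 0, Section 2.3.1 says: "The ECG will be reviewed by a cardiologist who will determine the clinical significance of any ECG abnormalities". Outside Section 2.3.1, the syndrome is named only in the package insert (Appendix B, Warnings).

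**The concern.** A categorical safety commitment appears in the risk section, while the list that sites work from does not carry it. No step has staff compare a candidate with Section 2.3.1.

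The wording of criterion 1 makes this more than a matter of labels. A history is enough only for congestive heart failure. The other cardiac items must be present. A past diagnosis of Wolff-Parkinson-White syndrome therefore counts under criterion 1 only if the single scheduled ECG is judged clinically significant, or if another listed condition is also present.

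The stake is rare but serious. The insert warns that beta-blockade in patients who have the syndrome together with tachycardia has led to bradycardia severe enough to need a pacemaker, once after a starting dose of 5 mg. The first dose in this trial is one 60 mg extended-release capsule (Section 5.2). The insert cautions against comparing formulations milligram for milligram, so the two doses cannot be set directly against each other. Even so, a low dose is not a full safeguard.

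**Working it through.** The plan gives no figure on this point. The check is a comparison of texts, followed by an illustrative calculation.

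**Step 1. The six not-recommended conditions against Section 4.2.** Cardiac failure is read as congestive heart failure, and thyrotoxicosis as hyperthyroidism.

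| Condition in Section 2.3.1 | Where it is handled |
|---|---|
| Cardiac failure | 4.2, criterion 1 |
| Nonallergic bronchospasm | 4.2, criterion 2 |
| Diabetes | 4.2, criterion 2 |
| Thyrotoxicosis | 4.2, criterion 2 |
| Major surgery | Not in 4.2. Planned procedures are reported (2.3.1), and under 4.4.4 "Participants requiring significant surgery will be withdrawn from the protocol" |
| Wolff-Parkinson-White syndrome | Neither in 4.2 nor in a separate provision |

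The tally is 4 named + 1 handled elsewhere + 1 with neither = 6. Of the 19 exclusions, 0 name the syndrome.

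**Step 2. Path of a known case through Section 4.2.**

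- If the Visit 0 ECG is judged clinically significant, criterion 1 excludes.
- If the resting rate is below 55, criterion 1 excludes unless the site cardiologist reviews the medical history, finds no contraindication to propranolol and approves.
- If the rate is 55 or more and the ECG is not judged significant, criterion 1 has no cardiologist review of history, and only criterion 19 remains.

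The third path is the gap.

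**Step 3. Illustrative size.** The documents give no prevalence. Let p be the share of otherwise eligible candidates with a known history, assumed to lie between 0.0005 and 0.003, and let n be the number of participants. The expected number is n × p. The chance of at least one is 1 − (1 − p)^n.

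| Group | p | n × p | 1 − (1 − p)^n |
|---|---|---|---|
| All randomized, n = 200 | 0.0005 | 0.1 | 0.095 |
| All randomized, n = 200 | 0.003 | 0.6 | 0.452 |
| Propranolol arm, n = 100 | 0.0005 | 0.05 | 0.049 |
| Propranolol arm, n = 100 | 0.003 | 0.3 | 0.260 |

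These figures describe known histories before the ECG reading or criterion 19 has acted. They are an upper bound on the third path, not an estimate of it.

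**The case against.** The strongest reply is that the exclusion is already delivered in substance. Section 2.3.1 is itself protocol text, and under Section 14.12 "A protocol deviation is any noncompliance with the clinical trial protocol, GCP, or the MOP", so enrolling a known case would be a deviation whatever Section 4.2 says. History is taken at prescreening and at Visit 0. Every candidate has a 12-lead ECG read by a cardiologist. Criterion 19 is open to an investigator whom the same protocol has told that propranolol is not recommended in the syndrome. A case gets through only if all of these fail together. The prescreening script and the Manual of Procedures are not among the documents and may ask about the syndrome directly.

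That stands as a limit on size. It does not remove the mismatch, because the ECG reading and criterion 19 rest on judgement and the deviation rule acts only after the event.

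Four narrower points also deserve an answer.

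- The insert's warning concerns the syndrome with tachycardia and is not among its contraindications. A resting candidate with an unremarkable ECG may well be at lower risk. This is accepted.
- Dosing starts at one capsule daily, and heart rate and blood pressure are measured at Visit 2, when the dose doubles, and at later visits. This helps, but it cannot prevent a first-dose event.
- Cardiogenic shock, from the contraindication list, is not named in Section 4.2 either. This is true. The tally above is confined to the six not-recommended conditions.
- A known history is broader than having the condition. This is also true, and it is the purpose of the change: without it, criterion 1 still depends on how one ECG is read.

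**Conclusion.** The concern holds. Section 2.3.1 states an exclusion as certain, and the list applied before randomization does not contain it. The omission is plain from the text. How often it would matter is not known.

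The practical gap is limited to a known case with a rate of 55 or more, an ECG not judged significant, and an investigator who does not invoke criterion 19. On the assumed 0.05% to 0.3%, fewer than one of 200 participants would have a known history at all, and the existing safeguards would probably catch most of those.

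This is a minor alignment of safety text that the sponsor should consider. It has no bearing on sample size, type I error or the analysis.

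**What to change.** Add one term to exclusion criterion 1 in Protocol Section 4.2: *known history or ECG evidence of Wolff-Parkinson-White syndrome*. No other change is needed.

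The cost is one term and IRB approval of the amendment, with no new test or visit, because history and ECG are already collected at Visit 0. On the assumed range, fewer than 1 of 200 participants would be affected. The change helps only while enrolment continues, and SAP Section 8.3.2 shows that some participants had already been enrolled when it was written.
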